2 INTRODUCTION AND BACKGROUND

Ulcerative colitis (UC) and indeterminate colitis are chronic inflammatory gastrointestinal disorders, which are limited to the colon and characterized by the involvement of the mucosa only (in contrast to the transmural inflammation seen in CD). UC primarily affects young adults (20 - 40 years) but may present also at a very early age (5-10 years) or in later in life (>60 years). The inflammatory process in UC and IC is primarily localized to the rectum (proctitis) or can extend proximally in a contiguous manner involving the mucosa up to the splenic flexure (left sided colitis) or involving the entire colon (extensive colitis). A key clinical feature of UC and IC is bloody diarrhea. The clinical course of UC and IC is characterized by periods of spontaneous exacerbation (acute flares) and remission (50 - 80% of patients) while some patients have a continuous active disease course (15 - 30% of patients) and others develop severe colitis (5 - 10% of patients), which can result in colectomy if medical therapy is not effective. Long standing UC and IC is associated with an increased risk of colorectal cancer; the use of 5-ASA products may reduce this risk. UC and IC can also be associated with inflammation involving extra-intestinal sites such as the skeletal, skin, or biliary system.

A “defunctioning” loop ileostomy is routine to the practice of colorectal surgery. In general, this type of ileostomy is put in place to direct the enteric contents away from a newly created surgical anastomosis that is downstream (distal) to the ileostomy. For example, a defunctioning loop ileostomy is routinely made during ileal pouch anal anastomosis (IPAA) surgery to facilitate healing of the IPAA. It is common practice to leave the diverting ileostomy in place for 8 to 12 weeks with the idea that this interval is needed to ensure complete healing of the anastomosis. After 8 to 12 weeks, an imaging study (e.g. contrast enema) is performed to confirm complete healing of the anastomosis. After that, so long as healing of the anastomosis has occurred, the diverting ileostomy is surgically reversed. While potentially beneficial to the healing process, a diverting ileostomy may also be detrimental to the health and well-being of the patient. Potential detriments include dehydration, leakage from the ileostomy with resultant skin irritation and interference with activities of daily living, ileostomy dysfunction, and its negative impact on both physical and emotional function and quality of life. In an ideal situation, the diverting ileostomy would be left in place for an adequate period to facilitate healing of the anastomosis, while closing the ileostomy at the earliest appropriate time point in order to minimize the risks associated with an ileostomy.

The primary outcome variable for the study will be the Comprehensive Complication Index (CCI). The CCI is a novel continuous scale to measure surgical morbidity that has been developed in the past few years. (Slankamenac, 2013) It is based upon a survey of patients, nurses, and surgeons measuring their perceptions of the seriousness of 30 postoperative complications common in abdominal surgery (Slankamenac, 2011). From this survey, a score between 0 (no complications) and 100 (death) was developed to measure the occurrence of one or more

Timing of Ileostomy Closure after Ileal Pouch Surgery

postoperative complications in abdominal surgery patients, taking into account the number and seriousness of the complications. The score has been validated using four different methods (K. Slankamenac, 2013), and has been applied to the databases from 3 different randomized surgical trials and shown to be useful in reducing required sample sizes in surgical clinical trials (K. Slankamenac, 2014)

Quality of life and functional outcomes of IPAA in patients with ulcerative colitis have been evaluated in retrospective studies. (Delaney 2003, Farouk 2000) The SF-12 is a validated quality of life measurement tool that has been used to evaluate patients who have undergone colorectal resection.

JUSTIFICATION AND OBJECTIVES OF THE CLINICAL TRIAL

Randomized prospective trials have evaluated the outcomes of standard (8 weeks) and decreased (8-13 day) intervals to defunctioning ileostomy reversal after rectal cancer surgery and have demonstrated superiority of decreased interval to closure. [Danielsen 2017; Alves 2008] The unique significance of our study is that it will focus on ulcerative colitis patients who undergo ileal pouch surgery with temporary defunctioning ileostomy.

This operation is performed on a minimum of 15 patients, with UC or IC, annually at University of Colorado Hospital and at the co-investigator centers. This surgery is performed by fellowship-trained and board certified colorectal surgeons at the University of Colorado.

Hypothesis: In patients with ulcerative or indeterminate colitis who undergo ileal pouch anal anastomosis and diverting loop ileostomy (IPAA) surgery* a short interval to loop ileostomy reversal will result in differences in complications and quality of life compared to a long interval to loop ileostomy reversal.

*For clarification, please see illustrations and images at end of this document

Aim #1: To compare the Comprehensive Complication Index (CCI), the incidence of postoperative complications, including total number of complications per patient, percent of patients with complications, and total number of ostomy-related complications per patient among IPAA patients who have their ileostomy reversed after a short interval compared to a long interval.

Aim #2: To compare the short vs. long interval groups on measures of health-related quality of life (SF-12) and IPAA functional outcomes

3 PATIENT SELECTION

Inclusion criteria

- Signed informed consent
- Patient age 18 to 64 years
- Confirmed or presumed diagnosis of ulcerative colitis or, indeterminate/undetermined colitis*
- Patient will be scheduled for non-emergent proctocolectomy or completion proctectomy with ileal j-pouch anal anastomosis (IPAA) and loop ileostomy (IPAA).
- Clinical assessment of patient after IPAA surgery indicates that patient is suitable for early ileostomy reversal

Exclusion criteria

Patients who meet one of the following criteria are to be excluded from the trial:

- Age < 18 or > 64 years
- Body mass index (BMI) equal or above 40 kg/m²
- Crohn's disease or suspected Crohn's disease
- Known previous or concurrent malignancy (other than that considered surgically cured, with no evidence for recurrence for 5 years). A recent history of basal cell or squamous cell carcinoma does not exclude the subject.
- Pregnant patients and female patients who do not satisfy the standard of care requirements of participating centers for an elective surgical procedure.
- Hemodynamic instability (persistent pulse rate < 50 or > 120 bpm, systolic blood pressure < 90 or > 160 mm Hg, uncontrolled cardiac arrhythmia, or active vasopressor drug use)
- Systemic sepsis
- Organ transplant recipient (e.g. Liver, Kidney, Pancreas)
- Immunosuppression due to chemotherapy drug use or systemic disease.
- Prednisone dose > 20 mg per day (or equivalent other steroid dose) within 4 weeks of scheduled IPAA
- Patients with ongoing C. difficile colitis
- Patients with pre-existing hepatic disease and portal hypertension

Timing of Ileostomy Closure after Ileal Pouch Surgery

- Patients with pre-existing renal dysfunction (creatinine >1.7 mg/dl)
- Patients with poorly controlled pre-existing chronic lung disease
- Therapeutic anticoagulation or coagulopathy (PTT or INR above normal range)
- Blood Hemoglobin < 8 g/dl
- Serum Albumin < 2.5 g/dl
- Clinical assessment of patient after IPAA surgery indicates that patient is not suitable for early ileostomy reversal
- Participation in another clinical trial within the last 30 days, or simultaneous participation in another clinical trial
- Well-founded doubt about the patient's cooperation
- Individualized decision by the surgeon to exclude the patient based on sound surgical judgment

Overview of time sequence

1. PHASE 1 (-30 to 0 days): Screening Visit and Informed Consent #1:

Assessment and documentation of initial inclusion and exclusion criteria will occur during the IPAA preoperative assessment clinic visit. A brief oral and written description of the trial will be presented to subjects who satisfy the initial inclusion/exclusion criteria and express interest in participation. These patients will be asked to review and sign informed consent #1 for SLIRPS trial participation. Case report form-1 (CRF-1, screening) will be completed at this time. The assessment will be performed by the study surgeon or study assistant at each site.

2. PHASE 1 (day 0): IPAA Surgery (See Illustrations at end of protocol):

- a. The use of a mechanical and/or oral antibiotic bowel preparation will be the discretion of the study surgeon, and will be documented in the appropriate study form. The same will apply to the preoperative use of intravenous prophylactic antibiotics and venous thromboembolism prophylaxis. “pre-IPAA” data points of interest will be recorded in CRF 2 by the study surgeon or trial assistant within 3 days of IPAA surgery.
- b. The IPAA surgery, including ileostomy creation, will be performed by the study surgeon in a manner that is consistent with accepted and standard surgical practice. The use of laparoscopic, hand-assisted laparoscopic, robotic, open, or other surgical techniques will be at the discretion of the study surgeon and will be recorded in CRF-3 (IPAA surgery details) by the study surgeon or trial assistant within 3 days of the IPAA surgery.

3. **PHASE 1 (day 5 to 12): IPAA Clinical Assessment:** On day **5-12** after IPAA surgery, the surgeon performs a routine “clinical assessment” of the patient and determines if the patient is suitable or not suitable for early ileostomy closure. (CRF 4, IPAA Assessment).
 - a. Study patients judged not suitable for early ileostomy closure are excluded from the study. Documentation of the reasons for “unsuitability” will be captured on CRF-4 (IPAA assessment).
 - b. Study patients judged suitable for early ileostomy closure will be asked for informed consent to participate in the trial.
4. **PHASE 2 (day 5 to 12): INFORMED CONSENT #2:** Study patients judged clinically suitable, by the study surgeon, for early ileostomy closure, will be asked to review and sign informed consent #2 for SLIRPS trial participation. Oral and written description of the trial will be presented to subjects who satisfy the inclusion criteria and initial and secondary exclusion criteria and express interest in participation. Consent will be obtained by the study surgeon or assistant at each site. After informed consent is obtained, the patient will be registered into the trial.
5. **PHASE 2 (day 5 to 12): IPAA Radiological Assessment** will be performed on **day 5-12** after IPAA on all study patients who are determined by the study surgeon to be clinically suitable for early ileostomy closure and who have provided informed consent (#1 and #2) to participate in the trial.
 - a. Radiologic assessment will be performed at day **5 to 12** after IPAA ostomy surgery. CT or fluoroscopic imaging of the IPAA with a water-soluble contrast medium will be performed to visualize the IPAA and determine the presence of radiologic leak. With either imaging modality, the enema contrast medium is instilled using a soft catheter.
 - b. **Subjects not radiologically suitable for early ileostomy reversal:** Study patients with a radiological leak from the IPAA will **not be randomized** to early or late closure. Details of the radiologic leak will be captured in CRF-4 (IPAA assessment). The patient will not be randomized to control or experimental trial arms. Treatment of these patients will follow the standards of care.
 - c. **Subjects radiologically suitable for early ileostomy reversal:** Study patients with no radiologic leak from the IPAA will be randomized to the control or experimental study arms. (CRF-4)
6. **PHASE 2 (day 5 to 12): RANDOMIZATION:** Immediately after IPAA radiologic assessment, study patients with no radiologic leak will be randomized to early (post-IPAA day 7 to 12) or late (post-IPAA \geq 8 weeks) ileostomy closure via the REDCap data collection system. The randomization scheme will be established by the study biostatistician. The randomization will be stratified by study site. Within each site, randomly

Timing of Ileostomy Closure after Ileal Pouch Surgery

selected block sizes of 2, 4, or 6 will be used so that the site investigators cannot predict beforehand the group to which the patient will be randomized.

7. PHASE 2 (day 7 to 12 or week 8-12): Ileostomy Closure:

- a. Early ileostomy closure will be performed at 7 to 12 days after IPAA.
- b. Late ileostomy closure will be performed 8 - 12 weeks after IPAA.
- c. The ileostomy closure surgical technique is at the discretion of the surgeon.
- d. CRF-5 (ileostomy reversal details) will be completed within 3 days of ileostomy reversal surgery.
- e. Endoscopic examination (optional): Rigid and/or flexible endoscopic examination of the IPAA may be performed per standard practice/standard of care, including non-study-related informed consent, at the discretion of the study surgeon following standard of care. (CRF-5)

8. PHASE 2 (day 7 – 12 to 6 months): Outcome assessment:

- a. The Comprehensive Complication Index and postoperative complications will be assessed and recorded by the study surgeon or trial assistant after review of the medical record, conversation with patient, and members of the care team (when appropriate). This assessment and documentation will begin immediately after randomization is performed and will be updated at 1-2 month intervals until 6 months after randomization. (CRF-6)
- b. Functional outcomes and quality of life (CRF-7): IPAA functional outcomes and quality of life (SF-12) will be assessed and recorded once at 6 months after ostomy reversal.

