Criteria for exclusion:	
 • Age < 18 or > 64 years • Body mass index (BMI) equal or above 40 kg/m² • Crohn's disease or suspected Crohn's disease • Known previous or concurrent malignancy (other than that considered surgically cured, with no evidence for recurrence for 5 years). A recent history of basal cell or squamous cell carcinoma does not exclude the subject. • Pregnant patients and female patients who do not satisfy the standard of care requirements of participating centers for an elective surgical procedure. • Hemodynamic instability (persistent pulse rate < 50 or > 120 bpm, systolic blood pressure < 90 or > 160 mm Hg, uncontrolled cardiac arrhythmia, or active vasopressor drug use) • Systemic sepsis • Organ transplant recipient (e.g. Liver, Kidney, Pancreas) • Immunosuppression due to chemotherapy drug use or systemic disease. • Prednisone dose > 20 mg per day (or equivalent other steroid dose) within 4 weeks of scheduled IPAA • Patients with ongoing C. difficile colitis • Patients with pre-existing hepatic disease and portal hypertension • Patients with pre-existing renal dysfunction (creatinine >1.7 mg/dl) • Patients with poorly controlled pre-existing chronic lung disease • Therapeutic anticoagulation or coagulopathy (PTT or INR above normal range) • Blood Hemoglobin < 8 g/dl • Serum Albumin < 2.5 g/dl • Clinical assessment of patient after IPAA surgery indicates

Timing of Ileostomy Closure after Ileal Pouch Surgery

	
that patient is not suitable for early ileostomy reversal
 
 Participation in another clinical IBD drug trial within the last 30 days, or simultaneous participation in another clinical trial Well-founded doubt about the patient's cooperation Individualized decision by the surgeon to exclude the patient based on sound surgical judgment
Criteria for Evaluation:	A confirmed or presumed diagnosis of ulcerative or indeterminate/undetermined colitis will be determined by the study surgeons. The diagnosis will be based on the constellation of clinical, endoscopic, and pathology results that are used in routine practice to establish a diagnosis of these conditions.
Primary variables	Comprehensive Complication Index at 6 months after randomization.

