- Injury to surrounding structures (specify, enterotomy, ureter injury, pelvic hemorrhage, etc.)
- Sepra Film wrap of ileostomy
- Epidural anesthesia

PHASE 1: IPAA Clinical Assessment

- Post-IPAA day that clinical assessment was performed
- Review / confirmation of inclusion exclusion criteria

Timing of Ileostomy Closure after Ileal Pouch Surgery

- Informed consent #2 obtained (only for patients determined to be clinically suitable for early ileostomy reversal)
- Not ready ileostomy reversal (explanation-comment and Clavien Dindo classification if applicable)

PHASE 2: IPAA Radiological Assessment

- Post-IPAA day that radiologic assessment was performed
- CT with rectal contrast (yes or no)
- Contrast enema (yes or no)
- Radiologic exam OK (Yes or No)
- Randomization to early or late ileostomy closure study arms
- Radiologic exam not OK and patient will NOT be randomized to experimental or control trial arms (explanation required)
- Explanation for no randomization
- Radiologic leak (yes or no, if yes, Clavien-Dindo classification if applicable)
- Other reason for no randomization

PHASE 2: Ileostomy Closure

- Duration of surgery (cut to close, minutes)
- Stapled ostomy closure
- Sutured ostomy closure
- Ostomy site skin complete closure
- Ostomy site skin partial closure (e.g. pursestring)
- Ostomy site skin not closed
- Endoscopic examination of IPAA (no, yes, comments)

PHASE 2: Outcome Assessment

- IPAA stenosis requiring more than simple digital dilation
- Small Bowel Obstruction (imaging confirmed)
- Ileus

Timing of Ileostomy Closure after Ileal Pouch Surgery

- Venous Thromboembolism
- Lung or Heart-related complications
- Hemorrhage requiring transfusion
- high output ileostomy
- Peristomal skin irritation
- Peristomal infection
- ileostomy prolapse
- ileostomy stenosis
- ileostomy revision necessary
- ileostomy leakage
- ileostomy dysfunction

Readmission

- Total # of inpatient hospital days
- Total # of hospital admissions

Comprehensive Complication Index: web-based calculation

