- Ileus: inability to tolerate normal oral intake by 72 hours after IPAA or ostomy reversal and/or radiologically confirmed in a patient with clinical signs of ileus
- Venous Thromboembolism: new diagnosis of upper or lower extremity of mesenteric vein VTE or pulmonary embolism after IPAA or ostomy reversal

Timing of Ileostomy Closure after Ileal Pouch Surgery

- Lung or heart-related complications: include new diagnosis of cardiac arrhythmia, coronary artery disease, congestive heart failure, pneumonia, pneumonitis after IPAA or ostomy reversal
- Hemorrhage requiring transfusion: pRBC administered after IPAA or ostomy reversal
- High output ileostomy: Regular use of antiperistaltic drugs required to control ileostomy output volume
- Peristomal skin irritation: irritation of the peristomal skin that resulted in pain, interference with activities of daily living (ADL), or unplanned treatments
- Peristomal infection: peristomal cellulitis or abscess requiring incision and drainage or unplanned ostomy surgery or antibiotic therapy
- Ileostomy prolapse: ileostomy prolapse that interferes with ileostomy pouching and/or ADL or requires surgical treatment
- Ileostomy stenosis: ileostomy stenosis that causes ileostomy dysfunction and/or interferes with ADL or requires surgical treatment
- Ileostomy revision necessary: unplanned ileostomy surgical treatment required
- Ileostomy leakage: persistent or recurrent ileostomy appliance leakage that interferes with ADL and requires more than ordinary measure to control
- Ileostomy dysfunction: dysfunction of the ileostomy that causes extraordinary problems with output, pouching, intestinal blockages, or otherwise interferes with ADL more than is usual and expected.
- Reoperation: any unplanned reoperation within 6 months of IPAA surgery
- Readmission: Any unplanned hospital readmission within 6 months of IPAA surgery
- Postoperative complication occurrence will be assessed via medical record review, discussion with study surgeon, other care givers, and study patient and recorded (CRF-6) at an interval of every 1 month until 6 months after randomization. Postoperative complication severity will be scored according to the Clavien-Dindo (CD) classification of surgical complications (Dindo, 2004, **Table**) The Comprehensive Complication Index will be calculated for each patient at 6 months after randomization.

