Appendix

Table: Clavien-Dindo Classification (From Reference #1)

[figure not shown]
TABLE 1. Classification of Surgical Complications

Grade	Definition
Grade I	Any deviation from the normal postoperative course without the need for pharmacological treatment or surgical, endoscopic, and radiological interventions Allowed therapeutic regimens are: drugs as antiemetics, antipyretics, analgesics, diuretics, electrolytes, and physiotherapy. This grade also includes wound infections opened at the bedside
Grade II	Requiring pharmacological treatment with drugs other than such allowed for grade I complications Blood transfusions and total parenteral nutrition are also included
Grade III	Requiring surgical, endoscopic or radiological intervention
Grade IIIa	Intervention not under general anesthesia
Grade IIIb	Intervention under general anesthesia
Grade IV	Life-threatening complication (including CNS complications)* requiring IC/ICU management
Grade IVa	Single organ dysfunction (including dialysis)
Grade IVb	Multiorgan dysfunction
Grade V	Death of a patient
Suffix "d"	If the patient suffers from a complication at the time of discharge (see examples in Table 2), the suffix "d" (for "disability") is added to the respective grade of complication. This label indicates the need for a follow-up to fully evaluate the complication.

[figure not shown]
*Brain hemorrhage, ischemic stroke, subarachnoidal bleeding, but excluding transient ischemic attacks.
CNS, central nervous system; IC, intermediate care; ICU, intensive care unit.

Timing of Ileostomy Closure after Ileal Pouch Surgery

Illustrations:

2-stage IPAA with (loop) ileostomy

Timeline study visits

Procedure	Timing	Location and/or individual responsible
Inclusion/exclusion criteria assessment	PHASE 1: During IPAA preoperative assessment	Surgical outpatient clinic / Surgeon or trial assistant
Informed Consent #1: obtained from patients who meet initial inclusion and exclusion criteria		
Case Report Form (CRF)-1 completion (Screening)	PHASE 1: During IPAA preoperative assessment	Surgical outpatient clinic / Surgeon or trial assistant
Case Report Form (CRF)-2 completion (Pre-IPAA details)	PHASE 1: Within 2 days of IPAA	REDCap application / Surgeon or trial assistant
IPAA surgery	PHASE 1: At discretion of patient and surgeon and within 30 days of inclusion/exclusion criteria assessment	Study site operating room / surgeon

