Case Report Form (CRF)-3 completion (IPAA surgery details)	PHASE 1: Within 2 days of IPAA surgery	REDCap application / surgeon or assistant
Post-IPAA clinical assessment	PHASE 1: Day 5 to 12 after IPAA	Study site inpatient setting / Surgeon
Exclusion of potential study patients judged not clinically suitable for trial entry. Case Report Form (CRF)-4 (IPAA Assessment)	PHASE 1: Day 5 to 12 after IPAA	REDCap application / Study site inpatient setting / Surgeon
Informed Consent #2 - obtained only from potential study patients who are clinically suitable for early ileostomy reversal	PHASE 2: Day 5 to 12 after IPAA, after IPAA clinical assessment	Study site inpatient setting / Surgeon
Radiologic imaging assessment of the IPAA	PHASE 2: Day 5 to 12 days after IPAA	Study site radiology suite
Case Report Form (CRF)-4 completion (IPAA Assessment) - finish	PHASE 2: Day 5 to 12 after IPAA, after IPAA radiological assessment	REDCap application / Study site inpatient setting / Surgeon
Randomization - of study patients who are radiologically suitable for early ileostomy closure	PHASE 2: Day 5 to 12 days after IPAA	Study site trial coordinator office / trial assistant
Ileostomy Closure	PHASE 2: Experimental Arm: 7 to 12 days after IPAA surgery Control Arm: \geq 8 weeks after IPAA surgery	Study site operating room

Timing of Ileostomy Closure after Ileal Pouch Surgery

Case Report Form (CRF)-5 completion (ostomy reversal details)	PHASE 2: Within 2 days of ostomy closure	REDCap application / surgeon or assistant
Outcome Assessment #1- Case Report Form (CRF)-6 (complications)	PHASE 2: 0-1 month after randomization.	REDCap application / surgeon or assistant
Outcome Assessment #2- Case Report Form (CRF)-6 (complications)	PHASE 2: 1-2 months after randomization.	REDCap application / surgeon or assistant
Outcome Assessment #3- Case Report Form (CRF)-6 (complications)	PHASE 2: 2-3 months after randomization.	REDCap application / surgeon or assistant
Outcome Assessment #4- Case Report Form (CRF)-6 (complications)	PHASE 2: 3-4 months after randomization.	REDCap application / surgeon or assistant
Outcome Assessment #5- Case Report Form (CRF)-6 (complications)	PHASE 2: 4-5 months after randomization.	REDCap application / surgeon or assistant
Outcome Assessment #6- Case Report Form (CRF)-6 (complications)	PHASE 2: 5-6 months after randomization.	REDCap application / surgeon or assistant

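### The operating surgeon, who knows the arm, may record and score the primary CCI for his or her own patients; deriving the grade from recorded treatment would narrow that discretion at small cost.

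*Combined protocol and SAP*

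**What the plan says.** Section 1 names the primary variable as "Comprehensive Complication Index at 6 months after randomization".

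On who produces it, Section 3, item 8a, states: "The Comprehensive Complication Index and postoperative complications will be assessed and recorded by the study surgeon or trial assistant". The Appendix timeline gives each of the six CRF-6 complication assessments to "REDCap application / surgeon or assistant". Section 3, item 2b, states: "The IPAA surgery, including ileostomy creation, will be performed by the study surgeon". Under items 3 and 4 the surgeon also judges whether the patient is suitable for early closure.

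On how events are found, Section 5 states: "Postoperative complication occurrence will be assessed via medical record review, discussion with study surgeon, other care givers, and study patient". On grading, the same section states: "Postoperative complication severity will be scored according to the Clavien-Dindo (CD) classification". It does not name the person who scores. Section 4 ends its outcome list with "Comprehensive Complication Index: web-based calculation".

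The Appendix reproduces the Clavien-Dindo table, which separates grades largely by what was done for the patient. Grade II, for example, is "Requiring pharmacological treatment with drugs other than such allowed for grade I complications".

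The masking in Sections 8 and 9 keeps results by treatment group from investigators during the trial. It does not concern whether the person completing CRF-6 knows a patient's arm.

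**The concern.** The person who operated and declared the patient fit for early closure may also decide which events go on CRF-6 and what grade they carry, knowing the arm. The document does not call the trial open, but the design makes it so for site staff: one arm has the stoma closed within 12 days of pouch surgery and the other keeps it for at least 8 weeks.

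Eight of the 14 complications listed under Outcome Assessment in Section 4 relate to the stoma, and the late arm is exposed to them for far longer. Discretion over those events therefore falls unevenly on the two arms. If grading leans one way in one arm, the difference in mean CCI is biased, in a direction that cannot be known in advance. More patients would not correct it.

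The web calculator does not help here, because it only combines grades that someone has already assigned.

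**Working it through.** **1. Where judgement enters the score**

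| Step | What the plan provides | Discretion left |
|---|---|---|
| Event found and counted | Written definitions (Section 5), several sources of information | Yes: ileostomy dysfunction and leakage, for example, are defined against what is ordinary |
| Treatment given | Left to each center (Section 6) | Yes |
| Grade assigned | Clavien-Dindo table (Appendix), scorer not named | Yes, but the table turns mainly on drug class, transfusion or parenteral nutrition, intervention with or without general anesthesia, ICU care, organ dysfunction and death |
| Grades combined into CCI | Web-based calculation (Section 4) | Little, but no recomputation from the grades is specified |

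The third and fourth steps can be turned into rules with little effort. The first two cannot.

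**2. The plan's sample size, as the baseline**

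Inputs from Section 10: difference 10 points, SD 20 to 22, alpha 0.05, power 80%. Equal allocation is implied by the equal group sizes.

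n per group = 2 × (1.960 + 0.842)² × SD² / 10²

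- SD 20: 63 per group, 126 in total.
- SD 22: 76 per group, 152 in total.

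Both match the plan with a two-sided test. A one-sided test would give 50 and 60, so the plan's figure is two-sided.

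**3. What misgrading would do**

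Section 10 equates 10 CCI points with one Clavien-Dindo grade. Let f be the share of one arm graded one grade off, all in the same direction. The document gives no value for f. The bias is b = 10 × f points.

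Standard error: SE = SD × √(2/n) = 20 × √(2/63) = 3.56. With SD 22 and n = 76 it is 3.57.

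Type I error = Φ(−1.96 + b/SE) + Φ(−1.96 − b/SE)

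Power when the bias opposes a true 10-point effect = Φ((10 − b)/SE − 1.96)

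| f | Bias (points) | Type I error | Power |
|---|---|---|---|
| 0 | 0 | 5.0% | 80% |
| 10% | 1 | 5.9% | 71% |
| 20% | 2 | 8.7% | 61% |

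The SD 22, n = 76 design agrees to within 0.2 percentage points. The calculation uses the two-means approximation behind the sample size rather than the planned log-link model, and it takes the SD as unchanged by misgrading. The CCI's own grade weights are not in the document and were not used.

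**The case against.** The strongest reply is that the plan already holds much of a rule-based derivation: written definitions for most listed events, several sources including the patient and the record, monthly CRF-6 assessments in the timeline, a published grading table and a calculated score. Surgeon assessment is permitted, not required, and surgeon grading is inferred because the scorer is not named. The trial assistant is no more masked than the surgeon; the timeline has the assistant carrying out randomization. All of this stands, and it limits what the fix can claim.

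Four stronger readings are tempting, and the document does not support them.

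- A reader might infer that programmed grading would remove most of the unmasked judgement. It would not. Deciding whether an event counts, and whether to treat it, both come before grading and stay with unmasked staff.
- A reader might infer that the grade needs no judgement once treatment is recorded. Grade I still rests on what departs from a normal postoperative course, the Grade I drug list needs interpretation, and organ dysfunction is a clinical call.
- A reader might infer that a site-entered CCI cannot be checked. Section 5 has severity scored by grade, and Section 9 provides cross-form checks, queries and an audit trail. The supportable statement is that no recomputation is specified.
- A reader might put the bias as high as 4 points by supposing that 10-20% of patients have a discretionary minor event worth 5-20 points (0.10 × 5 = 0.5; 0.20 × 20 = 4.0). Those inputs are not in the document, and the figure describes one-sided recording of events, which grading rules do not touch.

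**Conclusion.** The point holds in a limited form. The plan lets the operating surgeon assess and record the complications and the primary CCI for his or her own patients with the arm known, provides no masked or independent grading, and does not specify that the score is recomputed from its grades. Because the Clavien-Dindo table works mainly from treatment received, the grading part of that discretion can be narrowed cheaply, and should be.

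The size is illustrative only: 1-2 points against a 10-point target if 10-20% of one arm is misgraded by one grade in a consistent direction. It rests on that assumed fraction and on the plan's equivalence of one grade to 10 points. Nothing in the document shows that such misgrading would occur, or which arm it would favor. The planned 126-152 patients are not in question.

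**What to change.** Change Section 3, item 8a, and CRF-6 as follows.

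- The trial assistant enters, for each event, the onset date and the treatment received: drugs beyond the Grade I list, transfusion or parenteral nutrition, intervention without or with general anesthesia, ICU care, single or multiple organ dysfunction, death.
- The operating surgeon may clarify facts but does not assign the grade.
- REDCap derives the Clavien-Dindo grade from these fields by the Appendix table.
- The biostatistics team computes the CCI from the grades by program, replacing site entry of the score.

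The cost is a few fields in an existing form, one script, and slightly more data entry per event. It assumes that each center has an assistant able to complete CRF-6, which the document implies but does not state outright. Sample size and patient care do not change.

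The plan should also state the limit openly: event-finding and treatment decisions remain unmasked.
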